### 3. LIST OF ABBREVIATIONS AND DEFINITIONS OF TERMS

Abbreviation	Definition
AE	Adverse Event
B. Braun	B. Braun Medical Inc.
CP	Conditional Power
CRBSI	Catheter Related Bloodstream Infection
CRF	Case Report Form
CSR	Clinical Study Report
ED	Emergency Department
EDC	Electronic Data Capture
FDA	Food and Drug Administration
GCP	Good Clinical Practice
ICF	Informed Consent Form
ICH	International Conference on Harmonization
ITT	Intent to Treat
IRB	Institutional Review Board
ISO	International Organization for Standardization
LAR	Legally Authorized Representative
MITT	Modified Intent to Treat
PA	Peripheral Advantage
PICC	Peripherally Inserted Central Catheter
PIVC	Peripheral Intravenous Catheter
PP	Per Protocol
RN	Registered Nurse
SAE	Serious Adverse Event
SAP	Statistical Analysis Plan
SAS	Statistical Analysis System
SD	Standard Deviation
SOP	Standard Operating Procedure
US	United States
WHO	World Health Organization

## 4. INTRODUCTION

Peripheral intravenous catheters (PIVCs) are used to deliver medication and fluids directly into the bloodstream. The placement of PIVCs is the most common invasive hospital procedure. In the US alone, 60% to 90% of hospitalized patients require an IV catheter (Helm, 2015). Despite this large medical demand for PIVCs, there is a high failure rate and large cost associated with replacing the catheter due to complications. Therefore, there is a clinical unmet need to improve PIVC first stick success by developing a clinical education program.

B. Braun Medical Inc. is developing the Peripheral Advantage (PA) Program which includes the PA Education Curriculum; Christie VeinViewer® Vision2; Introcan Safety® IV Catheters; and STEADYCare™ Smallbore Extension Set to improve patient care at the bedside and decrease PIVC-associated complications, resulting in increased catheter indwell time and improved financial outcomes.

This study is designed to assess the effect of the B. Braun Peripheral Advantage (PA) Program that includes clinician education and specific B. Braun peripheral intravenous catheter (PIVC) therapy products designed to improve the clinical outcomes associated with a PIVC.

This Statistical Analysis Plan (SAP) is intended to prospectively (*a priori*) outline the analyses and presentations of data that will form the basis for conclusions to be reached to answer the study objectives outlined in the protocol and to explain in detail how the data will be handled and analyzed, adhering to commonly accepted standards and practices of biostatistical analysis in clinical trials. Results obtained from the analyses outlined in this document will be the basis for the clinical study report (CSR) and or publications for this study. This plan is based on Version 1.0 of the study protocol, dated 11 July 2019 and the Protocol Amendment 1 dated 03 February 2021.

## 5. STUDY OBJECTIVES

### 5.1. Primary Objectives

The primary objective of this study is to evaluate the impact of the B. Braun PA Program on the incidence of complications associated with PIVC use.

### 5.2. Secondary Objectives

The secondary objectives of this study are to evaluate the effect of the B. Braun PA Program on catheter indwell time, first stick success rates (first stick success), and aggregate costs associated with catheter insertion.

## 6. INVESTIGATIONAL PLAN

### 6.1. Overall Study Design and Plan

This is a single sequence multi-center study to evaluate the effectiveness of the B. Braun PA Program on improved clinical outcomes by decreasing PIVC complications, increasing PIVC indwell time, improving first PIVC stick success and improving estimated aggregated costs utilizing B. Braun PA.

The study will be divided into 4 Stages: three (3) clinical stages and one (1) interventional (educational) Stage. The four (4) Stages are: Baseline (Stage 1), Intervention/Education (Stage 2), Run-In (Stage 3), and Post-Interventional (Stage 4). The three (3) clinical stages (Baseline, Run-In, and Post-Interventional) require patient care which includes daily follow-up care for the catheter. The Intervention (education) stage (Stage 2) may include all RNs from the ED and/or the medical surgical floor(s)/unit(s) of the hospital. The Stage 2 intervention and the Stage 3 run-in will not involve any study patients.

The study will be conducted in the Emergency Department (ED) and/or Medical Surgical (MS) floor(s)/unit(s) in multiple hospitals. All RNs from these floors may participate in Stage 1 and Stage 2 of the study. A core group of RNs (Study RNs) on all shifts who have completed the institution's required clinical study training and required study protocol training will participate in Stage 1. These Study RNs will be responsible for PIVC insertions and monitoring in Stage 1.

The Study RNs from Stage 1 and all RNs from the medical/surgical unit(s) or ED who have met all study requirements and also completed the Peripheral Advantage Program specific training/intervention (Stage 2) will participate in Stage 3 and Stage 4 of the study. These Study RNs will be responsible for PIVC insertions and monitoring in Stage 4. Non-Study RNs should not perform any study related procedures (i.e., catheter insertion, site evaluations including documentation of both positive and negative findings, and catheter removal). In the event all RNs from the participating floor(s)/unit(s) are not able to participate in the study, the Investigator will take reasonable measures to ensure all study-related procedures are performed by the Study RNs.

A minimum of 632 successful PIVC placements are required to complete the study (316 successful PIVC placements in Stage 1 and 316 successful PIVC placements in Stage 4). Each study Stage must be completed before proceeding to the next study Stage. The final sample sizes of Stage 1 and Stage 4 will be determined by an interim analysis of raw data in each Stage.

The study will be conducted in compliance with this protocol, Good Clinical Practices (GCP), and any other applicable regulatory requirements.

#### **6.1.1. *Choice of Control Groups***

There is no control group in this study because it is a single-arm study. This is a single sequence study with Stage 1 (Baseline) followed by Stage 2 (Intervention), Stage 3 (Run-In), and Stage 4 (Post-Interventional).

#### **6.1.2. *Method of Assigning Subjects to Treatment Groups***

RNs from the medical surgical unit(s) or ED of the hospital can be on any shift and will not be required to have a minimum level of clinical experience. All participating RNs within the unit must complete the B. Braun Peripheral Advantage Program required trainings (Stage 2). Those RNs who have not completed all of the B. Braun Peripheral Advantage Program required trainings in Stage 2 cannot continue on to Stages 3 and 4 and thus will be removed from participation in the study. Study RNs should not be currently using the B. Braun Introcan Safety® IV Catheters, the STEADYCare™ Smallbore Extension Set or Christie VeinViewer® Vision2 utilized in this study.

### 6.1.3. *Blinding*

The study is an open-label study. Therefore, there is no blinding procedure applied in this study.

## 6.2. Description of Study Hypotheses

The primary hypothesis is that the rate or percentage of complications in the patients in Stage 4 utilizing the B. Braun Peripheral Advantage Program will be lower than the rate in the baseline at Stage 1 utilizing the site's current standard of care with regards to PIVC insertion technique used and Institution's PIVC type.

The study's null and alternative hypotheses are as follows:

$$H_0: P_{\text{Stage 4}} \geq P_{\text{Stage 1}}$$

$$H_a: P_{\text{Stage 4}} < P_{\text{Stage 1}}$$

where  $P_{\text{Stage 1}}$  and  $P_{\text{Stage 4}}$  represent the rate or percentage of complications in Stage 1 and Stage 4, respectively.

**Decision Criterion:** The null hypothesis will be rejected and the alternative hypothesis will be concluded if the upper confidence limit for the rate difference, i.e.  $P_{\text{Stage 4}} - P_{\text{Stage 1}}$ , of a 1-sided 95% confidence limit (normal approximation) is less than zero.

## 6.3. Study Endpoints

### 6.3.1. *Primary Efficacy Endpoint*

The primary endpoint for this study is the rate/percentage of complications (e.g., phlebitis/thrombophlebitis, occlusion, infection (localized or Catheter Related Bloodstream Infection (CRBSI), dislodgement or infiltration, extravasation, accidental removal, etc.).

### 6.3.2. *Secondary Endpoints*

The following acute secondary endpoints will be assessed:

- Indwell time for catheters with and without complications (measured in hours)
- First attempt insertion success rate (first stick success) for PIVC
- Rate of insertion of a Peripherally Inserted Central Catheter (PICC) or Midline Catheter due to inability to insert the PIVC or removal of the initial PIVC due to complications (rescue PICC or rescue Midline)
- Healthcare costs associated with PIVC use in a clinical setting.

## 7. DATA QUALITY ASSURANCE AND COMPUTING ENVIRONMENT

Case report forms (CRFs) for data collection were created in an Electronic Data Capture (EDC) system specifically for this study and were used to record data. The forms were completed by the study site personnel with oversight and approval by the Investigator. All procedures for the handling and analysis of data were conducted using GCP and meeting the International

Organization for Standardization (ISO) 14155 and the International Conference on Harmonization (ICH) guidelines and the US Food and Drug Administration regulations for the handling and analysis of data for Clinical Investigations.

All statistical analyses will be performed using the Statistical Analysis System (SAS) Software package, Version 9.4 or higher (SAS Institute, Cary, NC).

## 8. PATIENT POPULATIONS

The trial study population consists of male and female subjects eighteen (18) years of age or older with a medical condition that requires a PIVC anticipated to last for at least 48 hours. The subjects meet all inclusion criteria and do not meet any of the exclusion criteria described in Sections 4.1 and 4.2, respectively, of the study Protocol. Subjects in the patient population will be classified as 1 or more of the following based on their individual participation in the study:

- Screen Failure: Any subject who signed the Informed Consent or who's LAR provided consent and then the subject failed to meet the inclusion and or exclusion criteria,
- Enrolled: Any subject who signed the Informed Consent or who's LAR provided consent and then the subject met all of the inclusion and exclusion criteria, ,
- Early Termination: Any subject who was Enrolled but never had an attempted PIVC insertion or who was Enrolled and did not have a successful PIVC insertion by a study RN,
- Early Withdrawal: Any subject who was Enrolled, but who voluntarily withdrew their consent or was withdrawn by their LAR or was withdrawn by the PI,
- Study Completer: Any Enrolled Subject who had a successful PIVC insertion by a Study RN and had the PIVC removed for any reason

However, there will be three (3) analysis populations to be used in this analysis as described in Section 8.1.

### 8.1. Data Sets to be Analyzed

The following analysis populations have been defined for this study: an Intent-to-Treat (ITT) population, a Modified Intent-to-Treat (MITT) population, and a Per Protocol (PP) population.

#### Study Analysis Populations

Population	Subjects Included
ITT	The ITT population consists of all subjects who are consented, meet all of the inclusion criteria and none of the exclusion criteria, and are enrolled into the study.
MITT	The MITT population consists of all ITT subjects for whom treatment with the PIVC is attempted (successful or not successful).
PP	The PP population is a subset of the MITT analysis set who meet the following criteria: 
 
• there are no major deviations from the protocol eligibility criteria;
 

	
 
the subject receives a successful PIVC placement from a Study RN;
 
the subject has a primary efficacy endpoint assessment at Stage 1 and/or Stage 4.
 

--	--

The primary endpoint, the primary safety endpoint, and all secondary endpoint analyses will be carried out on available data in the MITT population; supportive analyses of primary endpoints will be carried out on the PP population as well. Demographic and safety summaries will be provided for the ITT and MITT populations, respectively.

## 8.2. Protocol Deviations

A study deviation is defined as an instance(s) of failure to follow, intentionally or unintentionally, the requirements of the study protocol, applicable laws or regulations, or the Investigator Agreement. No deviation from the protocol will be implemented by an Investigator without the prior review and approval by the sponsor. Such approval will be documented in writing and maintained in the study files. The Investigator must document and notify the sponsor of any deviation from the study protocol no later than five (5) working days after becoming aware of the deviation. Deviations to the protocol will be reported by the site to their Institutional Review Board (IRB), as required.

Major deviations include those that involve the primary endpoint, the informed consent process and the inclusion/exclusion criteria of the study, or any deviation that involves or leads to a serious adverse event in a study participant. The protocol deviations classified as Major include, at a minimum:

- Date and time of insertion/removal not recorded
- Informed consent
- Inclusion/Exclusion
- Failure to record daily observation of catheter
- Failure to record reason for catheter withdrawal

Under certain circumstances, deviations from the study protocol to protect the rights, safety and well-being of human subjects may occur. Such deviations shall be documented in writing and reported to the Sponsor and the IRB, if required, as soon as possible, and no later than five (5) working days.

Subject specific deviations will be reported on the Protocol Deviation CRF. Investigators will adhere to procedures for reporting study deviations to their IRB as required. Deviations from the clinical protocol will be reviewed and evaluated by the sponsor on an ongoing basis and, as necessary, appropriate corrective actions put into place.

## 9. STATISTICAL METHODS

### 9.1. Determination of Sample Size

Based on initial study design assumptions, at least 316 successful PIVC insertions are necessary to complete Stage 1 and at least 316 successful PIVC insertions are necessary to complete

Stage 4 in order to detect a statistically significant difference between the current standard-of-care products and B. Braun PA at 90% power and two-sided confidence level of 5.0%. The estimated complication rate in Stage 1 is 50% and the estimated complication rate in Stage 4 is 35% (Helm, 2015).

Two (2) interim analyses of raw data are planned solely for the purpose of sample size re-estimation. Using the method of Pocock & Mehta, the sample size can be either held constant or increased – it cannot be reduced based on the results of the re-estimation.

#### **9.1.1. *Interim Data Analysis Stage 1***

Upon successful completion of approximately 70% of the originally planned PICV placements in Stage 1, an interim analysis of the primary endpoint on uncleaned data will be performed. The observed complication rate in Stage 1, utilizing actual data collected in the study up to this point, will be compared to the originally estimated complication rate of 50%. If the observed complication rate is statistically significantly greater than 50%, the sample size will not be modified, and Stage 1 enrollment will continue to the original sample size of at least 316 successful PIVC insertions. If the observed complication rate is not statistically significantly greater than 50%, the sample size may be re-estimated with the assumed Stage 1 complication rate equal to the observed interim analysis complication rate, with other assumptions held constant.

#### **9.1.2. *Interim Data Analysis Stage 4***

The final sample size in Stage 1 (based on the results of the sample size re-estimation in Stage 1) will be used as the initial sample size for Stage 4. Upon successful completion of approximately 50% of the initial sample size in Stage 4 (which is determined at the interim analysis in Stage 1), another interim analysis on uncleaned data for the complications will be performed. This sample size re-estimation will follow the method of Mehta and Pocock to calculate the conditional power of the study to conclude that the complication rate in Stage 4 is lower than the complication rate in Stage 1, given the observed complication rates at the interim analysis. The conditional power (CP) will be categorized into one of the following three (3) zones:

- Favorable:  $CP \geq 90\%$
- Promising:  $41\% \leq CP < 90\%$
- Unfavorable:  $CP < 41\%$

In the event the conditional power is found to be in the Favorable or Unfavorable zone, the study will continue to the originally planned sample size in Stage 4 (i.e., final sample size in Stage 1). In the event the conditional power is in the Promising zone, the total study sample size may be increased to the required sample size to achieve conditional power of 90% at the completion of the study. Note that only the sample size in Stage 4 can be increased at this time, as the data collection in Stage 1 has been completed.

### **9.2. *General Considerations***

#### **9.2.1. *General Methods***

All descriptive statistical analyses will be performed using SAS (Version 9.4 or higher) unless otherwise noted. Derived variables will be programmed by the study programmer/statistician,

and then verified by an independent programmer/statistician. The program review also will include a check as to whether analyses conform to specifications of the SAP. All output will be incorporated into Microsoft Excel or Word files and formatted to the appropriate page size(s).

For categorical variables, the number and percentage within each category of the parameter will be calculated. For continuous variables, the N, median, mean, standard deviation (SD), minimum, and maximum values will be presented. Where appropriate, 95% two-sided confidence intervals may be presented.

If the observed data are found not to follow a normal distribution, appropriate non-parametric methods may be employed.

#### **9.2.2. *Adjustments for Covariates***

Adjustment for covariates such as years of nursing experience will be made.

#### **9.2.3. *Handling of Dropouts or Missing Data***

Every effort will be undertaken to limit premature discontinuations and ascertain completeness of data collection. All other analyses will utilize only actual subject data which is collected; no imputation of missing data will be performed.

#### **9.2.4. *Interim Analysis and Data Monitoring***

See Sections 9.1 and 9.2 for a description of the two (2) planned interim analyses of raw data for sample size confirmations. No other interim analysis is planned for this study at the time of protocol development. This study does not require and thus will not utilize a Data Monitoring Committee for monitoring the trial performance and the safety of enrolled subjects or an independent Clinical Events Committee (CEC) for endpoint adjudication.

#### **9.2.5. *Multicenter Studies***

Protocol Amendment 1 allows for multiple hospitals. Enrollment will be competitive across all study sites. In the event that more than one site is enrolling patients in the study, the stage by site interaction analysis will be performed to evaluate their heterogeneity in the rate of complications. Available data for all sites will be combined at Stage 1 and Stage 4, respectively, to perform analyses for the primary and the secondary endpoints.

#### **9.2.6. *Multiple Comparisons/Multiplicity***

This is a prospective, single-arm sequential study. Comparisons in the rate of complications will be performed between Stage 1 and Stage 4 by sites. There are no multiplicity adjustments.

#### **9.2.7. *Use of an Efficacy Subset of Patients***

Use of an efficacy subset of patients is not applicable to this study.

#### **9.2.8. *Active Control Studies Intended to Show Equivalence***

Active control studies intended to show equivalence are not applicable to this study.

#### **9.2.9. *Examination of Subgroups***

Exploratory analysis in the primary endpoint and secondary endpoints will be performed by site in this study.

#### **9.2.10. *Level of Statistical Significance***

All hypothesis tests will be one-sided and performed at the alpha=0.05 level. No adjustments to the alpha level will be made for the number of significance tests performed.

#### **9.2.11. *Visit Windows and Definitions***

There are no assessment windows at each stage in this study.

#### **9.2.12. *Subject Disposition, Demographics and Other Baseline Characteristics***

A tabulation of subject disposition will be presented including the screen failures, the number enrolled, the number of patients who successfully received a PIVC, the number of subjects who had PIVC durations  $\geq$ 48hrs and  $<$ 48hrs, the number of patients who completed Stage 1 and/or Stage 4, and the number of withdrawals, including reasons for withdrawal as documented on the CRF.

Baseline demographic characteristics will be summarized for Nurses and Patients in ITT population and MITT populations, respectively. Other available baseline characteristics will be reported as well.

#### **9.2.13. *Listing of Individual Data***

A by-subject listing of demographics, the primary and secondary endpoints, and adverse events may be provided.

### **9.3. Primary Endpoint Analysis**

The primary endpoint analysis will compare the rate/percentage of complications between B. Braun PA in Stage 4 and the hospital's current standard-of-care PIVC in Stage 1. The logistics regression will be used to estimate the differences while controlling the baseline characteristics such as years of nursing experience. Primary efficacy endpoint analysis will be performed at MITT and PP Populations, respectively. If 2 or 3 sites are used, this will be performed individually for each site and across all sites.

### **9.4. Secondary Endpoint Analyses**

Secondary endpoints that measure rates (e.g., first stick success and the rate of insertion of a Peripherally Inserted Central Catheter (PICC) or Midline Catheter) will be tested for significance between Stages 1 and 4 using a logistics regression while controlling the baseline characteristics such as years of nursing experience.

Both Indwell Times and Impact of using B. Braun PA on the healthcare costs associated with PIVC use will be compared between Stage 1 and Stage 4 using standard parametric tests (such as Student's t-test) or a non-parametric equivalent (such as Wilcoxon signed rank test) if parametric methods are found to be inappropriate. Appropriate regression models will likely be used to estimate the differences while controlling the baseline characteristics such as years of nursing experience.

A survival analysis by Kaplan Meier Curves between Stage 1 and Stage 4 will be performed to further understand the difference in time to any complication or failure of the unit. A catheter will be considered to have been a failure/event if it is removed due to any complication or failure of the device. It will be considered censored/non-event if it is removed as it is no longer

needed by the end of Stage 1 or Stage 4, i.e., the condition improves, or the subject is discharged from the hospital.

All secondary endpoint analyses will be performed in the MITT Population.

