### 12.2 Statistical Analyses for Secondary Endpoints

Standard statistical methods will be utilized in this study to analyze all data. Secondary endpoints that measure rates (e.g., first stick success) will be tested for significance using a binomial test (such as Fisher's exact test). Continuous endpoints will be tested for significance using standard parametric tests (such as Student's t-test), or non-parametric equivalent (such as Wilcoxon signed rank test) if parametric methods are found to be inappropriate.

Indwell Times: The source data are the indwell times measured for all catheters (e.g., catheter withdrawn due to complications, end of medical treatment, routine catheter change, end of treatment or voluntary withdrawal of subject from study). The indwell time is calculated from the time of catheter insertion until the time of catheter removal for any reason. In the event the subject or his/her LAR withdraws consent or is withdrawn by the PI, for any reason, and the catheter is still in place, the date and time of withdrawal will be used as a surrogate for the date and time of removal.

A survival analysis will be performed to further understand the difference in indwell times. A catheter will be considered to have been a failure/event if it is removed due to any

complication or failure of the unit. It will be considered censored/non-event if it is removed as it is no longer needed, i.e., the condition improves or the subject is discharged from the hospital.

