### **12.3 Safety Analyses**

Adverse events will be summarized as an overall incidence of at least one event, incidence within system organ class only, and incidence by system organ class and preferred term. Events may include, but are not limited to: minor and major complications, infection, thrombus, phlebitis, accidental needle sticks, and device failures (i.e., disconnection, twisted port hub, leakage, and failure of the safety feature). [Section 11](#) of this protocol details AE definitions and relationship classifications.

A Statistical Analysis Plan (SAP) will be prepared after the protocol and eCRF are approved. This document will provide further details regarding the definition of analysis variables and analysis methodology to address all study objectives. The SAP will serve as a complement to the protocol and supersedes it in the case of any differences.

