### **13.2 Data Handling**

In the event a subject with a successful PIVC insertion drops out or is withdrawn from the study, B. Braun or its designee will be informed in a timely manner and the date and time of withdrawal will be recorded. In the event a subject has or was withdrawn from the study before a PIVC insertion attempt or a successful PIVC insertion by a Study RN, he/she will be considered as an Early Termination from the study. In the event a subject or his/her LAR (if appropriate) withdraws consent or the PI removes the subject from the study for any reason, the subject will be considered as an Early Withdrawal. In the event of a subject's withdrawal of consent or any other early withdrawal that also did not result in the IV being removed, the date and time of that withdrawal will be used as a surrogate for the date and time of removal of the IV and the subject's data will be treated in the same manner as a study completer. In this case, the subjects will not be allowed to re-enroll in the study.

If the PIVC was removed for a complication, then the subject may not continue or re-enter into the study and he/she is considered a Study Completer. If the PIVC was removed as a result of treatment completions (i.e., subject no longer requires a PIVC) he/she will be considered a

Study Completer. In addition, if he/she was subsequently discharged from the facility, then he/she may re-enter the study in the same or different Stage if a re-admission for any reason is required.

Any data to be recorded directly on the eCRFs (to be considered as source data) will be identified at the start of the study. Data reported on the eCRF that are derived from source documents should be consistent with the source documents, or the discrepancies must be explained.

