## 10. CHANGES TO ANALYSES PLANNED IN THE PROTOCOL

There were no changes to the analyses planned in the protocol version 1.0 Amendment 1. However, due recruitment futility, this study was terminated prior to reaching Stage 2. Therefore, all analyses related to Stage 4 will not be performed.

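### The plan leaves open whether withdrawal with the catheter in place counts as removal in the Stage 1 indwell medians, and the SAP 9.4 event rule (removal) does not match the section's stated aim or the title of Figure 16.1

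*SAP*

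**What the plan says.** **Indwell time.** Protocol 12.2 defines it: "The indwell time is calculated from the time of catheter insertion until the time of catheter removal for any reason". The ways an indwell time can end, as listed there, include "routine catheter change, end of treatment or voluntary withdrawal of subject from study". For a subject who withdraws, or is withdrawn, with the catheter still in place, "the date and time of withdrawal will be used as a surrogate for the date and time of removal". Protocol 13.2 repeats this and adds that the subject's "data will be treated in the same manner as a study completer".

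**What the SAP does with that rule.** It does not mention it. SAP 9.2.3 says only collected data are used and missing data are not imputed. SAP 10 says "There were no changes to the analyses planned in the protocol". Protocol 12.3 sets the relation between the documents: "The SAP will serve as a complement to the protocol", and the same sentence gives the SAP precedence where the two differ. SAP 14 lists median indwell times in Tables 14.5.2 and 14.5.3 without naming an estimator.

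**Survival analysis.** SAP 9.4 says the Kaplan-Meier analysis is meant to show the time until a complication or failure. Its event rule is then: "A catheter will be considered to have been a failure/event if it is removed due to any complication or failure of the device". The only censoring it describes is removal because the catheter is no longer needed. SAP 16 titles Figure 16.1 as a Kaplan-Meier plot of complication onset. Protocol 12.1 records any complication and removal due to complication as two separate yes/no items.

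**What is still to be produced.** The study stopped before Stage 2, and SAP 10 states that "all analyses related to Stage 4 will not be performed". The two tables and the figure remain listed and can be produced from Stage 1 alone.

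**The concern.** There are two separate issues.

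1. When a subject leaves the study with a working catheter in place, all that is known is that the catheter lasted at least until then. That is a right-censored time. Entering it as an observed removal pulls the median down, and always in that direction.

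2. A complication and a removal for complication are different events, and the protocol records them separately. A figure titled as onset but built on the only stated event rule would leave out complications managed without removal and would date the others at removal. A reader would take it for the time course of complications, which it would not be.

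At stake is the correct reading of two descriptive tables and one figure, which are part of what the study can still deliver.

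**Working it through.** The plan gives no figure for either issue, so there is nothing to reproduce. I checked direction from the rules alone and size from stated assumptions.

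**Part 1: direction.** Let T be the true dwell and W the time of withdrawal in place. The surrogate rule records min(T, W). Since min(T, W) ≤ T for every catheter, no quantile can rise. This needs no assumption.

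**Part 1: size if withdrawal is unrelated to remaining dwell.**

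- Inputs: Protocol 1 gives typical dwell of 1.9 to 2.5 days, that is 1.9 × 24 = 45.6 h to 2.5 × 24 = 60 h. Treating these as medians is my assumption. The share w withdrawn in place is not in the documents; I take 2%, 5% and 10%.
- With exponential dwell at rate λ and withdrawal at rate μ, w = μ/(λ + μ), so λ + μ = λ/(1 − w).
- The recorded time is exponential at rate λ + μ, so its median is (1 − w) × ln 2/λ, which is (1 − w) times the true median.

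| w | true median 45.6 h | true median 60 h |
|---|---|---|
| 2% | 44.7 h | 58.8 h |
| 5% | 43.3 h | 57.0 h |
| 10% | 41.0 h | 54.0 h |

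A simulation of 200,000 catheters agrees: at 5% the surrogate medians were 43.3 and 57.0 h, and the Kaplan-Meier medians with withdrawal censored were 45.5 and 60.0 h. If the removal hazard rises with time (Weibull shape 2), the loss is smaller: at 5% and a 45.6 h median it is 1.57 h, or 1.57/45.6 = 3.4%.

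**Part 1: if withdrawal is related to remaining dwell.** Suppose withdrawal falls at a uniform point U of each catheter's own dwell. The surrogate survival is (1 − w)S(x) + w·P(UT > x). The censored Kaplan-Meier hazard is (1 − w)f(x) divided by that survival. With an exponential dwell, a 60 h median and w = 10%, the surrogate median is 4.53 h too short and the censored median 4.18 h too long. Over Weibull shapes 1 to 2 and w from 2% to 10%, the censored error is 44% to 92% of the surrogate error, with opposite sign. Censoring is therefore exact only under the independence assumption.

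**Part 2: the texts side by side.**

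| Place | What it refers to |
|---|---|
| SAP 9.4, purpose | time to a complication or failure |
| SAP 9.4, event rule | removal for complication or device failure |
| SAP 16, Figure 16.1 | onset of complication |
| Protocol 12.1 | complication and removal for complication, recorded separately |

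The event rule agrees with the purpose and the title only if every complication leads to immediate removal.

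*Complications without removal.* At the planned Stage 1 rate of 50% there are 50 complications per 100 placements. If 10% to 30% of them (assumed) do not lead to removal, 50 × 0.10 = 5 to 50 × 0.30 = 15 per 100 placements are not events.

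*Delay from onset to removal.* Take a median dwell of 52.8 h (2.2 days, the midpoint of the protocol's range), with complication and end of need equally frequent and exponential. Each then has a median of 2 × 52.8 = 105.6 h. A fixed lag L moves the Kaplan-Meier median to 105.6 + L and the event share to 0.5 × exp(−L × ln 2/105.6). For assumed lags of 6, 12 and 24 h the medians are 111.6, 117.6 and 129.6 h, and the event shares 48%, 46% and 43%, against 105.6 h and 50% for onset.

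**The case against.** The strongest reply is that the surrogate rule may not be in force. The SAP prevails where the documents differ, and SAP 9.2.3 limits analyses to collected data without imputation. A surrogate removal time can be seen as an imputation. The SAP 10 statement of no changes is weak support for carrying the rule over, because the SAP did change other things without declaring them: two-sided tests in Protocol 12 became one-sided in SAP 9.2.10, and the binomial test in Protocol 12.1 became logistic regression in SAP 9.3. The estimator for the median tables is unnamed, and SAP 13 places derivations in separate documents. All of this stands. A reader might infer that the Stage 1 medians will certainly be too short; the documents do not establish that. They contain one explicit rule for these catheters, and nothing that names or cancels it.

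On the figure, SAP 16 does not tie Figure 16.1 to the 9.4 rule, Figure 16.2 also speaks of onset, and onset of complication has a plain meaning. The figure may therefore be programmed correctly. What stands is that the SAP gives no onset-based event rule and that 9.4 contradicts its own aim.

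Protocol 12.2 also lists routine change and withdrawal, to which 9.4 gives no status. With the event defined, censoring is the natural reading, so this needs only a clarifying line.

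**Conclusion.** The concern holds as a minor one.

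- **Indwell medians.** If the protocol's surrogate rule is applied, the Stage 1 medians can only be shortened. The true size is unknown and may be negligible. Under exponential dwell and unrelated withdrawal, the proportional loss equals the share withdrawn in place.
- **Event definition.** The aim in SAP 9.4 and the title of Figure 16.1 do not match the only event rule stated. The illustrations of size rest on assumed lags and an assumed share of complications without removal.

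Two stronger conclusions are tempting and are not supported. One is that censoring cures the bias: it does so only if withdrawal is unrelated to remaining dwell, and otherwise it can err in the other direction. The other is that the program's evaluation is compromised: Stage 4 analyses are cancelled and these outputs are secondary and descriptive, so no test, primary result or stage comparison changes.

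**What to change.** 1. **Tables 14.5.2 and 14.5.3.** Report the Kaplan-Meier median indwell time with removal for any reason as the event and withdrawal in place censored at the withdrawal time. Give the number so censored and show the surrogate-rule median beside it. State that censoring assumes withdrawal is unrelated to remaining dwell and can otherwise overstate the median. Record the change in SAP 10.
2. **Figure 16.1 and SAP 9.4.** Either use the first recorded complication as the event, or retitle the figure as time to removal for complication or device failure; then align the 9.4 text. Protocol 6.1 has the site examined daily, so onset would be known to about a day, and only if dates were kept.
3. **Failure analysis in SAP 9.4.** State that withdrawal in place, routine change and any other removal not due to complication or device failure are censored.

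The cost is wording in SAP 9.4 and 10, a check or change to the programs for two tables, and a change to the program or title of one figure. No new data are needed unless onset dates were not kept, in which case retitling is the workable choice.
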